## **8 STUDY ASSESSMENTS AND PROCEDURES**

Study procedures and their timing are summarized in the SoA ([Table 2](#)). PRO assessment schedules are summarized in [Table 3](#).

The Investigator will ensure that data are recorded on the eCRFs. The Web Based Data Capture system will be used for data collection and query handling.

The Investigator ensures the accuracy, completeness, legibility, and timeliness of the data recorded and of the provision of answers to data queries according to the Clinical Study Agreement. The Investigator will sign the completed eCRFs. A copy of the completed eCRFs will be archived at the study site.

Immediate safety concerns should be discussed with the AstraZeneca representative immediately upon occurrence or awareness to determine if the participant should continue or discontinue IP.

Adherence to the study design requirements, including those specified in the SoA ([Table 2](#)), is essential and required for study conduct.

All screening evaluations must be completed and reviewed to confirm that potential participants meet all eligibility criteria. The Investigator will maintain a screening log to record details of all participants screened and to confirm eligibility or record reasons for screening failure, as applicable.

Procedures conducted as part of the participant's routine clinical management and obtained before signing of the ICF may be utilized for screening or baseline purposes provided the procedures met the protocol-specified criteria and were performed within the time frame defined in the SoA ([Table 2](#)).

Note: for laboratory assessments, if not all laboratory kits are available at a given visit, the Investigator should contact the Study Physician to confirm whether assessment is critical or may be postponed until supplies are available.

## **8.1 Efficacy Assessments**

### **8.1.1 Clinician-reported Outcome Assessments**

Investigators will complete clinician-reported outcome assessments during site visits in accordance with the SoA ([Table 2](#)). It is strongly encouraged to have the clinician-reported outcome assessments be performed by the same Investigator at each site to minimize variability in the assessments. The following assessments will be completed by the Investigator or designee: BP disease state ([Section 8.1.1.1](#)), BPDAI ([Section 8.1.1.2](#)), IGA ([Section 8.1.1.3](#)), [CCI](#) [REDACTED]

[CCI](#) [REDACTED] and healthcare resource utilization ([Section 8.1.1.7](#)).

Patient-reported outcomes assessments will be completed by the participants using an electronic PRO device ([Section 8.1.2](#)).

### 8.1.1.1 Bullous Pemphigoid Disease State

Investigators will be asked to make a clinical assessment of the participants to determine their BP disease state (ie, active disease, disease control, end of consolidation phase, remission, and relapse) from baseline (Visit 2) until the end of the double-blind period, during the OLE, and then in addition at the IPD, and follow-up visit. The BP disease state will be considered "active disease" until one of the disease states in [Table 6](#) is achieved.

At each visit, investigators will be required to assess a participant's outcome measures, including the states defined in [Table 6](#). The outcome measure will be documented in the eCRF.

**Table 6 Definitions for Bullous Pemphigoid Outcome Measures**

Outcome measure	Definition b
Disease control/beginning of consolidation phase	The time at which new lesions cease to form and established lesions begin to heal, or pruritic symptoms start to abate
End of consolidation phase	Time at which no new lesions have developed for a minimum of 2 weeks and approximately 80% of lesions have healed and pruritic symptoms are minimal
Sustained partial remission on minimal steroid a /off steroid therapy	The presence of transient new lesions that heal within 1 week while the participant is on minimal steroid therapy or off steroid therapy for at least 2 months
Sustained complete remission on minimal steroid a /off steroid therapy	The absence of new or established lesions or pruritus while the participant is on minimal steroid therapy/off steroid therapy for at least 2 months
Relapse	The appearance of 3 or more new lesions per month (blisters, eczematous lesions, or urticarial plaques) or at least one large (> 10 cm diameter) eczematous lesion or urticarial plaques that do not heal within 1 week, or the extension of established lesions or daily pruritus in participants who have achieved disease control

a Minimal steroid therapy is defined as less than or equal to 0.1 mg/kg/d of prednisone or equivalent

Definitions as per [Murrell et al 2012](#)

### Disease Control/Consolidation Phase

During the first 8 weeks of the study, participants will be assessed every 2 weeks for disease control (see [Table 6](#) for definition). When disease control is achieved, this marks the beginning of the consolidation phase. The end of the consolidation phase is the point that corticosteroid tapering will be initiated and documented in the eCRF.

## BP Remission

BP remission (see [Table 6](#) for definition) will be assessed at each study visit per the SoA ([Table 2](#)). Remission can be partial or complete and can occur off steroid therapy or on minimal steroid therapy.

## BP Relapse

In the event of a suspected BP relapse (see [Table 6](#) for definition), the participant should attend an unscheduled visit. A BPDAI evaluation will be conducted at the time of the relapse, or as soon as possible afterwards.

Investigators will be required to record details pertaining to each relapse event in the eCRF from baseline (Visit 2) until IPD visit/end of treatment and follow-up visit. Details should include the BPDAI activity and pruritus score and the required intervention(s), eg, OCS dose increase, the OCS dose at the time of relapse, addition of immunosuppressive therapy or requirement for hospitalization. Participants who require the addition of OCS after taper or an increase in the dose of OCS will be defined as having a relapse.

The management of participants who relapse will be according to standard of care. See [Section 6.5.1](#) for further details. The participant's relapse is managed with the addition of OCS and tapering should be recommended as soon as the relapse has been appropriately controlled as per current guidelines ([Feliciani et al 2015](#)). In case of a relapse during steroid tapering, the OCS dose may be increased to the previous dosage that symptoms were controlled. For recurrent relapses the OCS dosing regimen and tapering schedule will be at the Investigator's discretion. If the participant requires therapy other than OCS (eg, immunosuppressants), the study treatment may need to be discontinued but this should be discussed with the study physician prior to decision making. In the event that discontinuation of IP is required, the participant will still be asked to continue with the study assessments until the end of the double-blind period at Week 36. For relapse during OLE, the use of topical and/or oral corticosteroids and the schedule of taper will be at the discretion of the Investigator; however, it is recommended to follow the protocol taper schedule. The goal of therapy will be to taper off steroids to benralizumab monotherapy as soon as clinically indicated. In the event that the Investigator will need to control relapse with an immunosuppressant in the OLE, the participant will be withdrawn from the study and will not receive further benralizumab therapy. Participants may additionally be asked to allow future contact to provide follow-up clinical details regarding their health and information on disease state.

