#### 4.1.2 Double-blind Treatment Period

Approximately 120 eligible participants will be randomized 1:1 at baseline (Visit 2), to receive either benralizumab or placebo every 4 weeks (Q4W) by subcutaneous (SC) injection.

The randomization will be stratified by disease severity and time of BP diagnosis (participants with newly diagnosed BP; participants with a previous diagnosis of BP who have relapsed). Bullous pemphigoid disease area index (BPDAI) activity score will be used to assess disease severity, whereby participants with a score greater than or equal to 56 points will be classified as severe. The double-blind treatment period for each participant will last for 36 weeks.

Participants will receive a loading dose of either 60 mg benralizumab or placebo, administered as 2 SC injections at Visit 2. After 4 weeks, participants will receive 30 mg benralizumab or placebo Q4W per their initial randomization until the end of the double-blind treatment period. Starting at Visit 2, participants will also receive OCS 0.5 mg/kg/day until BP disease control is achieved. In participants who do not achieve disease control, the OCS dose can be increased (eg, 0.75 mg/kg; [\(Feliciani et al 2015\)](#) to achieve disease control. The steroid doses and time necessary to achieve disease control of BP may vary between participants.

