**Table 10 Primary and Key Secondary Estimands**

Statistical category	Treatment condition	Endpoint (Population)	Intercurrent event strategy	Population level summary (Analysis)
Key Secondary	Treatment with benralizumab versus placebo, regardless of IP compliance; rescue with OCS and restricted medication use indicate treatment failure	Change from baseline in BPDAI activity score at Week 36, change from baseline in BPDAI-Pruritus score at Week 36 (FAS)	

• Treatment discontinuation – treatment policy

• Rescue with OCSa – composite (LOCF)

• Restricted medication use – composite (LOCF)

• Study withdrawal – hypothetical (multiple imputation)

	Difference in mean change from baseline in BPDAI activity score/BPDAI-Pruritus score at Week 36 (ANCOVA)

a Rescue with OCS is defined as needing to increase OCS dose after previously having achieved disease control.

ANCOVA, analysis of covariance; BP, bullous pemphigoid; BPDAI, bullous pemphigoid disease area index; FAS, full analysis set; IP, investigational product; LOCF, last observation carried forwards; MMRM, mixed-effect model for repeated measures; OCS, oral corticosteroids.

The amount of missing data for this study is expected to be low, as participants who prematurely discontinue IP will be asked to come in for all visits and complete all study assessments up to the end of the study. Any participant with missing data at a specific time point will be considered as a non-responder at that time point.

Further estimands will be specified for the primary and key secondary endpoints to carry out sensitivity analyses for assessing the robustness of results. These sensitivity analyses will explore different methods for handling intercurrent events and different assumptions for missing data. Further description is given in Section 9.4.8 and will be fully specified in the SAP.

All analyses for the OLE endpoints will be descriptive, as no placebo-control data will be available for this period. Consequently, no hypothesis testing will be performed.

Demography and baseline characteristics will be summarized by treatment for the FAS. If there are major differences between the FAS and the safety analysis set, the summaries will be repeated and presented for the safety analysis set.

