#### **9.4.2.2 Analysis Methods for Key Secondary Efficacy Variables**

##### **Proportion of participants who remain relapse-free up to Week 36**

The proportion of participants who remain relapse-free up to Week 36 will be analyzed as a binary response variable, where participants who remain relapse-free throughout the study up to Week 36 will be considered responders, but otherwise participants will be considered non-responders. Relapse is defined as the appearance of: 3 or more new lesions per month (blisters, eczematous lesions, or urticarial plaques); or at least one large ( $> 10$  cm diameter) eczematous lesion or urticarial plaques that do not heal within 1 week; or the extension of established lesions or daily pruritus in participants who have achieved disease control.

The estimand strategy is outlined in [Table 10](#) above. Intercurrent events of rescue use with OCS after having previously achieved disease control, restricted medication use, and study withdrawal are unfavorable outcomes and will be handled with a composite strategy whereby participants experiencing these events prior to Week 36 will be considered as non-responders (ie, not relapse-free) in the analysis. Likewise, participants with missing data at Week 36 for any other reason will be considered as not-relapse free.

For the primary analysis of the proportion of participants relapse-free at Week 36, a logistic regression model will be fitted using a logit link function. The model will include treatment, baseline disease severity (moderate or severe, with a BPDAI activity score of 56 points used as the threshold between moderate and severe) and time of BP diagnosis (ie, participants with newly diagnosed BP versus participants with a previous diagnosis of BP who have relapsed) as categorical covariates.

The model will be used to estimate the proportion who are relapse-free for benralizumab and placebo, the difference between these proportions (benralizumab – placebo), a rate ratio

(benralizumab/placebo), and an odds ratio, with corresponding 95% confidence limits. A p-value, corresponding to a 2-sided test, will be presented to compare the benralizumab and placebo treatment groups. Note that if the logistic regression model does not converge to a solution due to low response rates in certain categories, the endpoint will be analyzed using a Cochran–Mantel–Haenszel test.

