3.1.5.2 Restricted medications

Restricted medications are detailed in the CSP Section 6.5.2 and will be selected considering a list of ATC codes that will be agreed and documented before unblinding (for the double-blind period) and final DBL (for the OLE period).

Only certain types of restricted medications used after randomisation during the double-blind period will be considered intercurrent events in the analyses, and only these cases will be handled as described in the estimand approaches detailed in Sections [4.2.6.1](#) and [4.2.6.2](#).

The restricted medications that will be considered intercurrent events include the following treatments if given to treat the participants BP, or if given for another condition but where prolonged use is deemed likely to substantially affect their BP outcomes:

- Immunosuppressive medications
- Anti-microbial agents with anti-inflammatory properties (eg. Tetracycline antibiotics, dapsone, erythromycin) – these are specific examples only, but review prior to unblinding will confirm if any others should be considered
- Topical corticosteroids
- Any marketed or investigational biologic (monoclonal or polyclonal antibody)
- Other IPs during the study or within 12 weeks after the last dose of benralizumab/placebo

In addition, for the endpoints where an increase in OCS use post disease control is considered an intercurrent event with consequence, this will only be in the case of OCS use with the aim of treating the participants BP, in a similar approach to the restricted medications described above. Short bursts of OCS use for other conditions (eg. COPD/asthma exacerbation) will not automatically trigger the estimand approach described.

A full review on concomitant medications will be performed prior to unblinding and the final list of intercurrent events will be confirmed and documented then.

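### Protocol 8.1.1.1 calls any OCS dose increase a relapse, which is wider than the endpoint definition, and SAP 3.3.1 has no rule to remove a relapse entered on that basis

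*Protocol*

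**What the plan says.** **The site instruction.** Protocol 8.1.1.1, under BP Relapse, states: "Participants who require the addition of OCS after taper or an increase in the dose of OCS will be defined as having a relapse". The first limb has a timing condition (after taper). The second has none, and neither limb mentions the reason for the OCS. The same text starts the recording of relapse details at Visit 2, when no participant has yet reached disease control on study.

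**The permitted early increase.** Protocol 4.1.2 says: "In participants who do not achieve disease control, the OCS dose can be increased". Section 6.5.1 repeats this.

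**The clinical definition.** Table 6 defines relapse by lesions and itch, with no steroid criterion. Its last limb reads "the extension of established lesions or daily pruritus in participants who have achieved disease control".

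**The analysis definition.** Table 10, footnote a: "Rescue with OCS is defined as needing to increase OCS dose after previously having achieved disease control". Protocol 9.4.2.2 applies this to the first key secondary endpoint: "Intercurrent events of rescue use with OCS after having previously achieved disease control, restricted medication use, and study withdrawal are unfavorable outcomes". SAP 3.1.5.1 also ties OCS rescue to the time after disease control. SAP 3.1.5.2 adds that the OCS must be aimed at BP: "Short bursts of OCS use for other conditions (eg. COPD/asthma exacerbation) will not automatically trigger the estimand approach described". SAP 3.3.1 applies both conditions when it counts an OCS increase as failure.

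**The concern.** Two definitions of a steroid-related relapse are in force. The one sites are told to use when completing the eCRF is wider than the one the estimand uses. If the wide one drives what is entered, participants who never relapsed can become non-responders.

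Relapse-free to Week 36 is the second test in the fixed sequence, and the four later key secondary tests depend on it. Relapse-free to Week 16 uses the same derivation. Time to first relapse counts from the earliest moment after randomization at which a relapse criterion is met, so an early false entry would count there as well. If the arms differed in how often OCS is raised before disease control, the endpoint would partly measure initial control rather than relapse. The documents do not say whether they would differ.

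**Working it through.** **Step 1. The definitions side by side.**

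| Place | Disease control first? | OCS given for BP? |
|---|---|---|
| Protocol 8.1.1.1, BP Relapse | Not required | Not required |
| Protocol Table 6 | Named in the last limb | No OCS criterion |
| Protocol Table 10 footnote and 9.4.2.2 | Required | Not stated |
| SAP 3.1.5.1 | Required | Not stated |
| SAP 3.1.5.2 and 3.3.1 | Required | Required |

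The 8.1.1.1 sentence is the only one with neither condition. The disease-control clause in Table 6 can be read as governing only its last limb, so it is not a dependable safeguard.

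**Step 2. The routes to failure in SAP 3.3.1.** Besides restricted medication, withdrawal and missing data, there are two:
- *OCS data.* An increase counts only after disease control and only if given for BP. By this route, neither a pre-control increase nor a burst for another illness is an automatic failure.
- *Recorded relapse.* SAP 3.3.1 restates the clinical definition and refers to SAP 3.2 for how disease states are collected, that is, as the investigator enters them in the eCRF. No stated rule sets aside a relapse entered before disease control, or one that rests only on an OCS increase.

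The pre-unblinding review in SAP 3.1.5.2 covers concomitant medications and the list of intercurrent events. It does not cover relapse entries. SAP Section 6, which lists changes from the protocol, does not mention 8.1.1.1.

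**Step 3. The plan's own figures, for context.** The documents power only the primary endpoint: 50% vs 20%, two-sided 5%, with 60 per arm for 90% (Protocol 9.2) and 50 per arm for 85% (SAP 1.3).
- Uncorrected, 90%: n = [1.96·√(2·0.35·0.65) + 1.2816·√(0.25 + 0.16)]² / 0.30² = 51.0, so 52.
- Continuity-corrected: (51.0/4)·[1 + √(1 + 4/(51.0·0.30))]² = 57.5, so 58.
- The same at 85%: 44 and 51.

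The corrected values agree with the stated 60 and 50 to within 2 per arm. No power is stated for the relapse-free endpoint.

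**Step 4. Illustration only.** Let *f* be the share of otherwise relapse-free participants, equal in both arms, who are recorded as relapsed. The observed rates are p(1 − f), so the difference shrinks by the factor (1 − f). None of the inputs is a planning value for this endpoint. Placebo rates of 20% and 33% are borrowed from the two relapse-free rates of the mepolizumab trial cited in Protocol 9.2, and the 30-point difference from the primary endpoint.

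Power (pooled z, 50 per arm) = Φ{[d − 1.96·√(2·p̄(1 − p̄)/50)] / √([p₁(1 − p₁) + p₂(1 − p₂)]/50)}. For f = 10% with 50% vs 20%: p₁ = 0.45, p₂ = 0.18, d = 0.27, p̄ = 0.315, giving Φ[(0.270 − 0.182)/0.0889] = 0.839.

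| f | Difference (points) | Power, placebo 20% | Power, placebo 33% |
|---|---|---|---|
| 0 | 30.0 | 0.894 | 0.863 |
| 5% | 28.5 | 0.868 | 0.827 |
| 10% | 27.0 | 0.839 | 0.787 |
| 20% | 24.0 | 0.770 | 0.700 |

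With 60 per arm and a 20% placebo rate, power is 0.941, 0.922, 0.900 and 0.842. The pooled z-test gives somewhat higher power than the corrected method of Step 3, so only the decline across rows is informative.

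**The case against.** The strongest reply is that the sentence should be read in context. It sits under a BP Relapse heading that opens by pointing to Table 6, and the text just before it lists a dose increase among the interventions for a relapse. Section 6.5.1 also refers to relapse as Table 6 defines it, and presents the early increase as a step towards control. On that reading a site would enter a relapse only for BP that worsens after control. Every statement of the endpoint (Protocol 9.1 and 9.4.2.2, SAP 3.3.1) defines relapse clinically, and none imports the 8.1.1.1 sentence. The eCRF instructions, which may settle the matter, are not in the documents.

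Much of this stands. The narrow reading is open to sites and may be the usual one, so misrecording is possible rather than certain. But the sentence is worded as a mandatory definition, its second limb has no qualifier, and recording starts before control. The statement in 8.1.1.1 that disease stays active until a Table 6 state is reached does not formally bar the entry either, because relapse is itself a Table 6 state. Where a site reads the sentence literally, nothing in the SAP corrects the result.

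**Conclusion.** Wrong as written. The 8.1.1.1 sentence contradicts Table 6, the rescue definition and the SAP's limit to BP-directed OCS, and it cannot be squared with the increase allowed before disease control. An entry made under it can reach relapse-free to Week 36, relapse-free to Week 16 and time to first relapse. How often is unknown: the documents give no rate of pre-control increases, of non-BP bursts or of miscoding, and the table in the working supports no estimate.

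A reader might infer more than the documents support:
- *That all such events will fail the endpoint.* They do not through the OCS-data route, and through the recorded-relapse route only if a site enters a relapse.
- *That steroid cover for adrenal insufficiency is caught.* Section 6.5.1 asks only that the condition be considered; it describes no OCS increase for it.
- *That cumulative time in remission off OCS is distorted.* A pre-control entry precedes any remission, and SAP 3.4.2 already ends the counted interval when OCS restarts.
- *That the bias has a known direction between arms.* Nothing in the documents says which arm would have more such increases.

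**What to change.** 1. Reconcile the 8.1.1.1 sentence with the definition the documents already use for this endpoint: OCS added or increased to treat BP after disease control. Put the same wording in the eCRF completion guidance, and have other increases recorded in the OCS form with their reason rather than entered as a relapse.
2. Before unblinding, compare all relapse entries with the OCS form, blinded to treatment. Query any with no earlier record of disease control, or where the coinciding OCS increase has a non-BP reason. Ask the site whether the clinical criteria of Table 6 were met.
3. State in SAP 3.3.1 how an entry is handled when the query shows that it rested on the OCS increase alone.

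The cost is a sentence in the protocol, a guidance note, a programmed listing and a small amount of extra data review. The check should cover entries made before the wording changes as well as after. No dose or treatment rule changes.
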